#### 11.4.2. Proportion of Subjects Experiencing Complications of Colds

##### Variables Used for the Analysis

The analysis will require the following variables:

**Table 8: Variables Used for Analysis of Complications of Colds**

Variable	Source	Format/Notes
Complications of colds	CRF	Investigators will designate an adverse event as a complication if the event meets protocol-specified criteria.

##### Analysis

Proportions of subjects experiencing one or more complications of colds will be compared between the treatment groups using a Fisher's exact test.

Analysis Population(s): ITTI

Derived Variables: None

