8.4. Statistical Methodology

The statistical methodology is described briefly below and will be described in detail in the Statistical Analysis Plan.

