8.4.1. Efficacy Analyses

Efficacy analyses will be based on a population consisting of all subjects that received at least one dose of study drug and had laboratory-documented EV/RV infection (infected intent-to-treat or ITTI population). Laboratory-documented EV/RV infection is defined by identification of EV/RV in nasopharyngeal secretions by RT-PCR at baseline, Day 2 or Day 3. For time to event analyses a test of significance (as described in the following) will be performed with descriptive statistics provided including the use of Kaplan-Meier figures.

There will be one primary efficacy analysis:

- Time to Symptom Response for the NTZ treatment group will be compared to that of the placebo treatment group using a stratified Gehan-Wilcoxon test ($\alpha = 0.05$) where stratification will follow that used for randomization. Subjects without a Symptom Response being recorded will be treated as censored as of their last diary without a documented Symptom Response.

If the primary analysis is significant at the 0.05 level, a key secondary efficacy analysis will be formally evaluated at the 0.05 level as follows:

- Time to Ability to Perform All Normal Activities for the two treatment groups will be compared using a stratified Gehan-Wilcoxon test ($\alpha = 0.05$) where stratification will follow that used for randomization. Subjects without an Ability to Perform All Normal Activities response being recorded will be treated as censored as of their last diary without a documented Ability to Perform All Normal Activities response.

If both the primary analysis and the key secondary efficacy analysis are significant at the 0.05 level, another secondary efficacy analysis will be formally evaluated at the 0.05 level as follows:

- Proportions of subjects experiencing one or more complications of colds due to EV/RV infection will be compared between the treatment groups using a Cochran-Mantel-Haenszel test stratified by the randomization strata ($\alpha = 0.05$).

Exploratory analyses will be performed as follows:

- For each of the 32 individual FLU-PRO symptoms, Time to Individual Symptom Response for the NTZ and placebo treatment groups will be compared using the Gehan-Wilcoxon test.
- For each of the 6 FLU-PRO domains, Time to FLU-PRO Domain Response for the NTZ and placebo treatment groups will be compared using the Gehan-Wilcoxon test.

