- Time to Return to Usual Health for the NTZ and placebo treatment groups will be compared using the Gehan-Wilcoxon test.
- Changes in viral titers from baseline to Day 2, from baseline to Day 3, and from baseline to Day 7 for the NTZ and placebo treatment groups will be compared using a t-test.
- For subjects with laboratory-confirmed EV/RV, the proportions of subjects with EV/RV detected by culture in nasopharyngeal swabs collected at each of Days 2, 3 and 7 will be compared for the two treatment groups using a Fisher's exact test.
- For the ITT population, Time to Symptom Response for the NTZ and placebo treatment groups will be compared using the Gehan-Wilcoxon test.
- For subsets of subjects infected with individual non-EV/RV viruses (e.g., coronavirus), Time to Symptom Response for the NTZ and placebo treatment groups will be compared using the Gehan-Wilcoxon test.

Sensitivity analyses for the primary endpoint will include:

- Repeat the primary efficacy analysis, assigning a Time to Symptom Response of 21 days for subjects that discontinue prior to Day 21 without achieving Symptom Response.
- Repeat the primary efficacy analysis for a "per protocol" subset.
- Repeat the primary efficacy analysis excluding NTZ-treated subjects who reported experiencing chromaturia.

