## 7. INTRODUCTION

The purpose of this statistical analysis plan (SAP) is to describe the planned analyses and data displays to be included in the Clinical Study Report (CSR) for Protocol RM08-3005.

All decisions regarding final analysis as defined in this SAP will be made prior to database lock and unblinding of the study data. Further information can be found in the protocol.

The SAP is based on:

- Protocol RM08-3005, Final Version 1.3, November 29, 2018
- International Conference on Harmonisation Guidelines E4 and E9; and
- Discussions with the U.S. Food and Drug Administration (FDA).

This document will describe analysis populations and detail methodology for deriving variables, handling missing data, and analyzing efficacy and safety data.

The SAP may be revised or amended to reflect the requirements of protocol amendments or regulatory requests, but must be finalized, approved and placed on file before the database is locked. Deviations from the SAP will be noted in the CSR.

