#### **11.2.2. Analysis of the Primary Efficacy Parameter**

The primary efficacy parameter, time to Symptom Response, will be derived as follows:

Event: Time of Symptom Response – time of the first dose

Censored: Time of last symptom assessment – time of the first dose

If Symptom Response is achieved at the time of the first symptom assessment diary record, the subject will be excluded from the analysis.

If Symptom Response is not achieved prior to a subject’s last available diary assessment, but the criteria are met at the last available diary assessment with no evidence of symptom relief medication intake during that diary period, time of Symptom Response will be considered to have occurred at the start of the last daily diary period.

Time to Symptom Response for the NTZ treatment group will be compared to that of the placebo treatment group using a Gehan-Wilcoxon test stratified by (1) time from onset of illness to time of first dose of study medication (0-24, >24-≤36, or >36 hours from onset), (2) pre-enrollment use of symptom relief medication, and (3) presence of underlying lung condition including asthma, COPD, or past or present history of smoking. The comparison will be graphically depicted using Kaplan-Meier curves.

Analysis Population(s): ITTI

Derived Variables: Event: Time of Symptom Response – time of first dose

Censored: Time of last symptom assessment – time of first dose

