### 11.4. Secondary Efficacy Analyses

If the primary analysis is significant at the 0.05 level, the secondary efficacy analysis of Time to Ability to Perform All Normal Activities will be formally evaluated at the 0.05 level. If the primary analysis and the secondary efficacy analysis of Time to Return to Normal Activities are both significant at the 0.05 level, the secondary efficacy analysis of Proportions of Subjects Experiencing Complications of Colds will be formally evaluated at the 0.05 level. If any of these analyses is not significant at the 0.05 level, the subsequent analyses or analysis will be performed as exploratory.

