### Analysis

The efficacy parameter, Time to Ability to Perform All Normal Activities, will be derived as follows:

Event: Time of Ability to Perform All Normal Activities – time of the first dose

Censored: Time of last ability assessment – time of the first dose

If Ability to Perform All Normal Activities is achieved at the time of the first ability assessment diary record, the subject will be excluded from the analysis.

If the subject does not achieve Ability to Perform All Normal Activities prior to the subject's last available diary assessment, but records a "10" for ability to perform all normal activities at the last available diary assessment with no evidence of symptom relief medication intake during that diary period, time of Ability to Perform All Normal Activities will be considered to have occurred at the time of the last available diary assessment.

Time to Ability to Perform All Normal Activities for the NTZ treatment group will be compared to that of the placebo treatment group using a Gehan-Wilcoxon test stratified

by (1) time from onset of illness to time of first dose of study medication (0-24, >24-≤36, or >36 hours from onset), (2) pre-enrollment use of symptom relief medication, and (3) presence of underlying lung condition including asthma, COPD, or past or present history of smoking. The comparison will be graphically depicted using Kaplan-Meier curves.

Analysis Population(s): ITTI

Derived Variables: Event: Time of Ability to Perform All Normal Activities – time of first dose

Censored: Time of last ability assessment – time of first dose

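### Complications, the third formally tested endpoint, has a stratified Cochran-Mantel-Haenszel test in the protocol and an unstratified Fisher's exact test in the SAP, with no reason given

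*SAP*

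**What the plan says.** Protocol 8.4.1 (Efficacy Analyses) compares the proportions with at least one complication by a "Cochran-Mantel-Haenszel test stratified by the randomization strata" at alpha 0.05. It does so only if the primary and key secondary analyses are both significant.

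SAP 11.4 keeps that third, gated place: "the secondary efficacy analysis of Proportions of Subjects Experiencing Complications of Colds will be formally evaluated at the 0.05 level". SAP 11.4.2 then names the test: "Proportions of subjects experiencing one or more complications of colds will be compared between the treatment groups using a Fisher's exact test". The population is ITTI, and no strata are mentioned.

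Three other places bear on how to read this:

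- SAP 7 gives its source as "Protocol RM08-3005, Final Version 1.3, November 29, 2018", which is the protocol version reviewed here.
- Protocol 8.4 introduces its methods with "The statistical methodology is described briefly below and will be described in detail in the Statistical Analysis Plan".
- For the first two formal endpoints the SAP keeps the protocol's stratified test. SAP 11.2.2 uses a "Gehan-Wilcoxon test stratified by (1) time from onset of illness to time of first dose of study medication" and two further factors. SAP 11.4.1 has NTZ "compared to that of the placebo treatment group using a Gehan-Wilcoxon test stratified" by the same three factors.

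**The concern.** A confirmatory step should have one pre-specified test, and here two documents name two. Running Fisher's test departs from the protocol. Running the Cochran-Mantel-Haenszel (CMH) test departs from the SAP, and SAP 7 requires such departures to be noted in the study report. If the mismatch is found after unblinding, either choice can look driven by the result.

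The choice can decide the formal outcome. With 5/300 against 14/300 subjects with complications, Fisher's exact test gives p = 0.059 and a single-stratum Mantel-Haenszel test without continuity correction gives p = 0.036.

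**Working it through.** **Comparison of the texts**

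| | Protocol 8.4.1 | SAP 11.4 and 11.4.2 |
|---|---|---|
| Endpoint | One or more complications of colds | Same |
| Population | Infected subset given at least one dose | Same (ITTI) |
| Place in sequence | Third, at 0.05 | Third, at 0.05 |
| Test | CMH by randomization strata | Fisher's exact, no strata |

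The SAP revision history mentions complications for the data source (v1.1), the analysis by symptom relief medication use (v1.2) and the ITT repeat (v1.3). It mentions the testing order in v1.3. No entry concerns the test. The three protocol amendments do not mention it either. The documents do not show when Fisher's test entered the SAP. The protocol's own use of Fisher's test is for an exploratory comparison, where culture-positive proportions "will be compared for the two treatment groups using a Fisher's exact test".

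**No figure to reproduce.** Neither document gives a complication rate, power or sample size for this endpoint. Protocol 3 (Choice of Endpoints) says only that too few complications are expected to show a difference. All rates below are assumptions.

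**Arm sizes.** Protocol 8.1 gives 600 infected subjects and a positive rate of at least 40%, so about 600/0.40 = 1,500 are enrolled, 750 per arm. ITTI is a PCR-positive subset, so its split is not fixed. If infection is independent of arm, the number in one arm is hypergeometric:

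- variance = 600 × 0.5 × 0.5 × (1,500 − 600)/(1,500 − 1) = 90.1, so SD = 9.5
- mean difference between arms = 15 subjects
- probability of exactly 300/300 = 4.2%

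**The example above.** With 19 events in 600 subjects, the expected count in one arm is 19/2 = 9.5. The variance is 300 × 300 × 19 × 581/(600² × 599) = 4.607. The statistic is (5 − 9.5)²/4.607 = 4.40, p = 0.036, against Fisher p = 0.059. The disagreement does not need equal arms: 5/295 against 14/305 gives 0.043 and 0.060.

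**Size of Fisher's test.** Two-sided, nominal 5%, by exact enumeration of two binomials averaged over the hypergeometric split:

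| Common rate | 2% | 3% | 5% | 8% | 10% |
|---|---|---|---|---|---|
| Size | 3.2% | 3.7% | 4.0% | 4.2% | 4.2% |

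**Power.** Fisher and uncorrected chi-square are exact, averaged over the split. CMH without continuity correction is simulated: 60,000 replicates per setting, Monte Carlo SE at most 0.2 points. It uses 3 × 2 × 2 = 12 strata with assumed shares of onset 60/30/10%, symptom-relief use 50/50% and lung condition 35%, and a threefold complication risk with lung condition.

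| Assumed rates | Fisher | Chi-square | CMH | Chi-square − Fisher |
|---|---|---|---|---|
| 3% vs 2% | 9.3% | 11.9% | 11.7% | 2.6 |
| 4% vs 2% | 25.6% | 29.8% | 29.5% | 4.2 |
| 5% vs 3% | 20.5% | 23.7% | 23.9% | 3.2 |
| 6% vs 2% | 68.9% | 72.7% | 72.3% | 3.8 |
| 8% vs 3% | 75.4% | 78.4% | 78.2% | 3.0 |
| 10% vs 4% | 81.3% | 83.6% | 83.9% | 2.3 |
| 2% vs 1% | 11.4% | 16.3% | not run | 4.9 |
| 1.5% vs 0.75% | 7.7% | 12.9% | not run | 5.2 |
| 1% vs 0.5% | 3.7% | 8.8% | not run | 5.1 |

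A separate enumeration matched the exact columns to within about 0.2 points.

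**Where the loss comes from.** Across lung-condition risk ratios of 1, 3 and 5, stratification itself changes power by −0.5 to +1.0 point. CMH minus Fisher is 1.8 to 4.4 points over the first six rate pairs. The loss is therefore mostly the discreteness of Fisher's test. For those six pairs the gap to chi-square is largest, 4.8 to 7.5 points, at exactly 300/300, which is an unlikely split.

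**Is CMH safe with sparse strata?** Its simulated size is 4.8 to 5.1% at rates of 2 to 10%, 4.6% at 1% and 2.2% at 0.5%. It does not inflate.

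**The case against.** The strongest reply has four parts.

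- **The SAP names exactly one test.** The protocol calls its own statistical text brief and leaves detail to the SAP, and SAP 7 requires analysis decisions before lock. So the SAP is not internally ambiguous. This stands, but replacing a named stratified test with an unstratified one is more than added detail, and neither document says which governs.
- **Fisher's test is a respectable choice for rare events**, which the protocol expects, and CMH also becomes conservative at a 0.5% rate. This stands as a reason the sponsor could give. The SAP does not give it.
- **The effect is minor.** The endpoint is last in sequence, is reached only after two significant results, and Fisher's test protects type I error. This stands and limits the weight of the point.
- **A loss of 2 to 4 points is too general a statement.** This is right for low rates, where the gap to chi-square is about 5 points, so the smaller range somewhat understates the loss there. Neither test has useful power at those rates.

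**Conclusion.** The concern holds. Protocol and SAP name different tests for one formally tested endpoint, and the difference is neither explained nor recorded. It should be settled before unblinding, and it does not threaten the trial's main conclusions. Type I error is not inflated. The cost of Fisher's test against the protocol's CMH test is about 2 to 4 power points at assumed rates from 3% vs 2% to 10% vs 4%. Against chi-square it is about 5 points at the three lower rate pairs checked.

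These sizes rest on assumed complication rates, 600 infected subjects from about 1,500 enrolled, and infection independent of arm. The CMH figures also rest on the assumed stratum shares and lung-condition risk. The textual discrepancy rests on none of these.

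**What to change.** Before unblinding, change SAP 11.4.2 to the protocol's CMH test stratified by the randomization strata, state whether a continuity correction is used, and keep Fisher's exact test as a supportive analysis. The exploratory ITT repeat in SAP 11.5.8 follows through its reference to 11.4.2. If the sponsor prefers Fisher's test as the formal one, SAP 11.4.2 should give the reason and the revision history should record it as a change from the protocol.

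One separate wording correction goes with this. SAP 8.2 describes randomization as stratified by time from onset to first dose, while Protocol 3 and 6 use onset to enrollment. SAP v1.2 records first-dose timing as a clarification of how the interval is calculated; that cannot alter how subjects were randomized. SAP 8.2 should describe the randomization factor as the protocol does, because a CMH test by randomization strata needs it stated correctly. No effect of this wording on results has been shown.

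The cost is SAP text and a few lines of programming. The strata should already be held by the central randomization procedure.

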#### 11.5. Exploratory Efficacy Analyses

##### 11.5.1. Time to Individual Symptom Response

###### Definitions:

Individual Symptom Response For each individual symptom (n=32), a score of ≤ the maximum response value specified by the Symptom Response definition maintained for at least two consecutive daily diary periods without symptom relief medication during or between those daily diary periods.

Time of Individual Symptom Response

The start of the first daily diary period in which Individual Symptom Response is achieved and is maintained for at least two daily diary periods without any symptom relief medication during or between those two daily diary periods.

Time to Individual Symptom Response	Time (hours) from the first dose of study medication to the Time of Individual Symptom Response.
-------------------------------------	--

#### Variables Used for the Analysis

The analysis will require the following variables:

**Table 9: Variables Used for Analysis of Time to Individual Symptom Response**

Variable	Source	Format/Notes
Date and time of first medication intake	CRF	
Date and time of completion for each symptom assessment record	Subject diary	
Symptom score assessment for each symptom for each diary record	Subject diary	
The ordinal symptom severity, intensity or frequency score assessment for each of the 32 symptoms will be coded to numerical values 0-4.
 
It will not be possible for any individual symptom assessment to be missing within a diary record, therefore no individual item imputation will be required.
 
In the event that the diary was not completed at a specified time point (e.g., Day 2), the missing data will not be imputed.

Date and time of symptom relief medication intake	Sponsor-provided listing	
The list of symptom relief medications will be selected from the listing of all concomitant medications prior to unblinding. Subjects will report the reason for taking each symptom relief medication, and this data will be used to assign concomitant medications to relevant cold symptoms reported in the FLU-PRO questionnaire.

#### Analysis

The efficacy parameter, time to Individual Symptom Response, will be derived as follows:

Event: Time of Individual Symptom Response – time of the first dose

Censored: Time of last symptom assessment – time of the first dose

If Individual Symptom Response is achieved at the time of the first symptom assessment diary record, the subject will be excluded from the analysis.

If the Individual Symptom Response is not achieved prior to a subject's last available diary assessment, but the criteria are met at the last available diary assessment with no evidence of symptom relief medication intake during that diary period, Time of

Individual Symptom Response will be considered to have occurred at the start of the last daily diary period.

Time to Individual Symptom Response for the NTZ treatment group will be compared to that of the placebo treatment group using a Gehan-Wilcoxon test stratified by (1) time from onset of illness to time of first dose of study medication (0-24, >24-≤36, or >36 hours from onset), (2) pre-enrollment use of symptom relief medication, and (3) presence of underlying lung condition including asthma, COPD, or past or present history of smoking. The comparison will be graphically depicted using Kaplan-Meier curves.

Analysis Population(s): ITTI

Derived Variables: Event: Time of Individual Symptom Response – time of first dose  
Censored: Time of last symptom assessment – time of first dose

### 11.5.2. Time to FLU-PRO Domain Response

### Definitions:

**FLU-PRO Domain Response** For each FLU-PRO domain (n=6), each item/symptom scored  $\leq$  the maximum response value specified by the Symptom Response definition and maintained for at least two consecutive daily diary periods without symptom relief medication during or between those daily diary periods

## Time of FLU-PRO Domain Response

The start of the first daily diary period in which FLU-PRO Domain Response is achieved and is maintained for at least two daily diary periods without any symptom relief medication during or between those two daily diary periods.

## Time to FLU-PRO Domain Response

Time (hours) from the first dose of study medication to the Time of FLU-PRO Domain Response.

### Variables Used for the Analysis

The analysis will require the following variables:

**Table 10:** Variables Used for Analysis of Time to FLU-PRO Domain Response

Variable	Source	Format/Notes
Date and time of first medication intake	CRF	
Date and time of completion for each symptom assessment record	Subject diary	

Variable	Source	Format/Notes
Symptom score assessment for each symptom for each diary record	Subject diary	The ordinal symptom severity, intensity or frequency score assessment for each of the 32 symptoms will be coded to numerical values 0-4.  In the event that the diary was not completed at a specified time point (e.g., Day 2), the missing data will not be imputed.
Date and time of symptom relief medication intake	Sponsor-provided listing	The list of symptom relief medications will be selected from the listing of all concomitant medications prior to unblinding. Subjects will report the reason for taking each symptom relief medication, and this data will be used to assign concomitant medications to relevant domains captured in the FLU-PRO questionnaire.

### Analysis

The efficacy parameter, Time to FLU-PRO Domain Response, will be derived as follows:

Event: Time of FLU-PRO Domain Response – time of the first dose

Censored: Time of last symptom assessment – time of the first dose

If FLU-PRO Domain Response is achieved at the time of the first symptom assessment diary record, the subject will be excluded from the analysis.

If the FLU-PRO Domain Response is not achieved prior to a subject's last available diary assessment, but the criteria are met at the last available diary assessment with no evidence of symptom relief medication intake during that diary period, Time of FLU-PRO Domain Response will be considered to have occurred at the start of the last daily diary period.

Time to FLU-PRO Domain Response for the NTZ treatment group will be compared to that of the placebo treatment group using a Gehan-Wilcoxon test stratified by (1) time from onset of illness to time of first dose of study medication (0-24, >24-≤36, or >36 hours from onset), (2) pre-enrollment use of symptom relief medication, and (3) presence of underlying lung condition including asthma, COPD, or past or present history of smoking. The comparison will be graphically depicted using Kaplan-Meier curves.

Analysis Population(s): ITTI

Derived Variables: Event: Time of FLU-PRO Domain Response – time of first dose  
Censored: Time of last symptom assessment – time of first dose

